4.1 Enrolment/screening period

4.1.1 Enrolment procedures

Enrolment procedures are described in Section 3.3. The screening period begins once the patient has signed the informed consent. Screening evaluations are described in Table 1 and Table 2.

4.2 Treatment period

AZD1775 will be administered orally as instructed by the Investigator or research staff. Patients will be eligible to continue to receive study treatment as long as they are continuing to show clinical benefit, as judged by the investigator, have no evidence of disease progression, and do not meet any criteria for discontinuation or withdrawal (see Section 3.9 and Section 3.9.1).

4.3 Follow-up period

Patients discontinuing AZD1775 should be scheduled for an End of Treatment (EOT) visit as soon as possible after their last dose. At that visit all assessments listed in the EOT visit column in Table 1 and Table 2 will be performed. If treatment is discontinued during a study visit, the EOT visit does not need to be repeated. The reason for stopping treatment and the date must be recorded in the electronic case report form (eCRF).

4.3.1 30-day safety evaluation

After discontinuation from AZD1775, patients must be followed for AEs for 30 days, after their last dose (see Section 6) or until new cancer therapy is started. This can be done via telephone contact at the Investigator's discretion. All concomitant medications received up to 30 days after the last dose of study medication should be recorded in the medical record and eCRF.

All new AEs occurring during this period must be reported and followed until resolution, unless, in the opinion of the Investigator, these values are not likely to improve because of the underlying disease. In this case, the investigator must record his or her reasoning for this decision in the patients' medical records and as a comment in the eCRF.

All patients who have Grade 3 or 4 laboratory abnormalities (per National Cancer Institute Common Terminology Criteria for Adverse Events [NCI CTCAE] v4.03 (<http://evs.nci.nih.gov/ftp1/CTCAE/CTCAE>), at the time of discontinuation must be followed until the laboratory values have returned to Grade 1 or 2, unless it is, in the opinion of the investigator, not likely that these values are to improve. In this case, the investigator must record his or her reasoning for making this decision in the patients' medical records and as a comment on the eCRF.

4.3.2 Follow-up period

4.3.2.1 Follow-up for patients who discontinue treatment prior to disease progression

Patients discontinuing from AZD1775 in the absence of PD should continue to have the progression-free survival (PFS) assessments performed according to [Table 1](#) or [Table 2](#) until PD has been assessed by the Investigator or the patient begins a new course of cancer therapy or withdraws from the study. If PD has been assessed patients, will then be followed for survival.

4.3.2.2 Survival follow-up

Patients with documented disease progression will be followed every 3 months for survival status (e.g., date and cause of death) for up to 2 years, death, or until time of final data collection for the progression-free survival analysis, whichever comes first. Patients may be contacted during outpatient visits or by telephone. Information pertaining to the type and dates of administered post-treatment therapy will be collected when available (see [Table 2](#)).

4.3.2.3 Final Protocol Visit and Beyond

The Final Protocol Visit (FPV) requirement applies only to patients who continue AZD1775 after the implementation of the Revised Clinical Study Protocol (CSP) Version 5.

Beyond the FPV, patients may continue to receive AZD1775 if they are deriving clinical benefit, in the opinion of the Investigator, and not fulfilling any of the discontinuation criteria. Such patients are to be treated in accordance with local practice and as deemed appropriate by the Investigator to ensure continued safety monitoring of the patient while receiving the investigational product. It is recommended to continue observing ongoing patients at the frequency indicated within the study plan as described in [Table 2](#). Restrictions regarding concomitant medications (refer to [Section 7.8](#)) will be followed while the patient is receiving AZD1775. A change in AZD1775 dose/schedule should only occur for safety reasons, based on the Investigator's judgement, and should generally follow the approach for dose reduction and discontinuation as described in this protocol. Combining AZD1775 with other systemic anti-cancer therapy is not allowed.

If a patient is no longer receiving benefit from AZD1775 beyond the FPV in the opinion of the treating physician, then the study drug should be stopped. The Investigator will inform AstraZeneca when a patient discontinues the study drug. Patients must return unused medication during routine clinic visits, and drug accountability information must continue to be collected in patient source documents until the patient discontinues treatment. In addition, provided that patient gives proper informed consent, a DNA blood sample for future biomedical research should be obtained at the time of AZD1775 discontinuation, if due to disease progression. Patients will continue to be monitored for all SAEs, pregnancies, and overdoses for 30 days after the last dose of the investigational product.

5. STUDY ASSESSMENTS

The Sarah Cannon Development Innovations, LLC (Innovations) Trial Master electronic data capture (EDC) system will be used for data collection and query handling. The investigator will ensure that data are promptly and accurately recorded on the eCRFs as specified in the study protocol and in accordance with the instructions provided.

The investigator ensures the accuracy, completeness, and timeliness of the data recorded and of the provision of answers to data queries according to the Clinical Study Agreement (CSA). The investigator will sign the completed eCRFs. A copy of the completed eCRFs will be archived at the study site.

5.1 Efficacy assessments

5.1.1 Tumour assessments

RECIST v1.1 criteria will be used to assess patient response to treatment by ORR and DCR. The RECIST v1.1 guidelines for measurable, non-measurable, target and non-target lesions (NTL) and the objective tumour response criteria (CR, PR, SD or progression of disease) are presented in [Appendix D](#).

The same method of assessment of tumour burden used at baseline (computed tomography [CT] scans or magnetic resonance imaging [MRI] of the chest and abdomen/pelvis) must be used at each subsequent follow-up assessment (see [Table 1](#) or [Table 2](#)). CT scan or MRI of chest and abdomen/pelvis are mandatory and must be repeated every 2-4 cycles.

Following the baseline assessment, efficacy for all patients will be assessed by objective tumour assessments every 6 weeks \pm 1 week after start of treatment until objective disease progression as defined by RECIST v1.1 or withdrawal from study.

Categorisation of objective tumour response assessment will be based on the RECIST v1.1 criteria of response: CR (complete response), PR (partial response), SD (stable disease) and PD (progression of disease). Target lesion progression will be calculated in comparison to when the tumour burden was at a minimum (i.e. smallest sum of longest diameters previously recorded on study). In the absence of progression, tumour response (CR, PR, or SD) will be calculated in comparison to the baseline tumour measurements obtained before starting treatment.

If the Investigator is in doubt as to whether progression has occurred, particularly with regard to NTLs or the appearance of a new lesion, it is advisable to continue treatment until the next scheduled assessment or sooner if clinically indicated, and reassess the patient's status. If repeat scans confirm progression, then the date of the initial scan should be declared as the date of progression.

To achieve 'unequivocal progression' on the basis of non-target disease, there must be an overall level of substantial worsening in non-target disease such that, even in presence of SD

or PR in target disease, the overall tumour burden has increased sufficiently to merit discontinuation of therapy. A modest ‘increase’ in the size of one or more (NTL) is usually not sufficient to qualify for unequivocal progression status.

It is important to follow the assessment schedule as closely as possible. Please refer to the study plan in [Table 1](#) or [Table 2](#). Patients will be assessed by standard criteria. For the purposes of this study, patients should be evaluated for radiographic tumour response every six weeks (± 1 week [cycle length dependent]). The same method of assessment and the same technique should be used to characterize each identified and reported lesion at baseline and throughout the study. Overall tumour response and progression will be calculated according to RECIST 1.1 (see [Appendix D](#)) at the designated time points.

Tumour status will be compared to baseline and confirmation of response will be evaluated by physical examination, anatomic imaging measurement, and performance status.

5.2 Safety assessments

5.2.1 Laboratory safety assessment

Blood samples for determination of clinical chemistry, haematology, coagulation, and PK will be taken at the times indicated in the Study Plan (see [Table 1](#) or [Table 2](#)).

Additional safety samples may be collected as clinically indicated and at the discretion of the Investigator. The date, time of collection and results (values, units and reference ranges) will be recorded on the appropriate eCRF.

The clinical chemistry and haematology will be performed at a local laboratory. Sample tubes and sample sizes may vary depending on laboratory method used and routine practice at the study centre.

The following laboratory variables will be measured as a minimum (some of these variables may be measured at baseline only):

Table 3 Safety Laboratory Variables

Haematology (2.7 mL whole blood sample)	Clinical chemistry (2.7 mL serum or plasma sample)
B-Haemoglobin	S/P-Albumin
B-Leukocyte	S/P-Alanine transaminase (ALT)
B-Haematocrit	S/P-Aspartate transaminase (AST)
B-Red blood cell count	S/P-Alkaline phosphatase (ALP)
B-Absolute leukocyte differential count	S/P-Bilirubin, total
Neutrophils	S/P-Calcium, total

Lymphocytes	S/P-Creatinine
Monocytes	S/P-Chloride
Basophils	S/P-Potassium
Eosinophils	S/P-Sodium
B-Platelet count	S/P-Urea nitrogen or blood urea nitrogen

Coagulation (1.8 mL sample)

B-PT or INR with PTT

Pregnancy test (Blood or urine)

The Investigator should make an assessment of the available results with regard to clinically relevant abnormalities. Any clinically significant abnormal laboratory values should be repeated as clinically indicated and recorded on the eCRF. The laboratory results should be signed and dated and retained at centre as source data for laboratory variables. For information on how AEs based on laboratory tests should be recorded and reported, see Section 6.4 and Section 6.5.

NB. In case a patient shows an AST or ALT $\geq 3x$ ULN and total bilirubin $\geq 2x$ ULN, please refer to [Appendix C](#) ‘Actions required in cases of combined increase of Aminotransferase and Total Bilirubin – Hy’s Law’ for further instructions.

5.2.2 Physical examination

A complete physical examination will be performed and include an assessment of the following: general appearance, respiratory, cardiovascular, abdomen, skin, head and neck (including ears, eyes, nose and throat), lymph nodes, thyroid, musculo-skeletal (including spine and extremities) and neurological systems at the times indicated in the Study Plan (refer to [Table 1](#) and [Table 2](#)).

If new or aggravated physical findings imply deterioration compared with baseline, the finding should be reported as an AE (Section 6.4.6). Performance status will be assessed using the ECOG performance status criteria (see Study Plan [[Table 1](#) and [Table 2](#)]).

5.2.3 Tumour assessments

Baseline tumour imaging studies (e.g., CT scans or MRI of the chest and abdomen/pelvis) will be performed within 28 days prior to the first dose of study drug and will be repeated at the completion of Cycle 2. The same method of assessment and the same technique must be used to characterize each identified and reported lesion at baseline and during subsequent imaging procedures. Tumour imaging studies will be repeated every 6 weeks to assess response. Patients continuing study treatment for a minimum of 1 year may have the tumour imaging assessments expanded to every 4 cycles (12 weeks [± 7 days]).

5.2.4 Electrocardiograms

All patients must have a screening 12-lead safety electrocardiogram (ECG) (paper ECG printout of 10 seconds for Investigator review) in order to meet eligibility criteria (see Section 3.2).

The patients in the Part A Safety Lead-in will have triplicate ECGs collected at each PK collection time point (see Table 1). Triplicate ECGs will be collected in Part B patients at baseline if clinically indicated (see Table 2).

Triplicate ECG recordings should be taken within an approximate 5-minute period. Additional ECGs may be taken at any other time the Investigator deems necessary for safety during the administration period. Twelve-lead ECGs will be obtained after the patient has been resting semi-supine for at least 10 minutes before the start of each recording and they must be in the same supine body position (maximum 30 degrees flexion in the hip and feet not in contact with the footboard) at the recording time point; except for the baseline ECG following the administration of AZD1775. For each time point during the PK collections for Part A, 3 ECG recordings should be taken at approximately 2-5 minutes interval. The mean QTcF interval for all 3 ECGs must be ≤ 450 msec for male patients and ≤ 470 msec for female patients prior to the initiation of treatment. A standardised ECG machine should be used and the patient should be examined using the same machine throughout the study if possible.

Part A - ECGs will be obtained before the PK blood collection as follows: Screening, Cycle 1 Day 1 and on Cycle 1 Day 3 or Day 10. ECG collected from time (h) post AZD1775 dose: pre-dose, 1h, 2, 4, 6, 8 and 12h post dose. Repeated ECGs should be performed on the same equipment if possible.

Part B - Patients will have ECGs performed at screening and baseline as indicated in the Study Plan detailed in Table 2. Patients consenting to the PK blood collections will have ECGs performed before the PK collection pre-dose and at 2-4 hours post dose as outlined in Table 2 and repeated only if clinically indicated.

After paper ECGs have been recorded, the Investigator will judge the overall interpretation as normal or abnormal. If abnormal, it will be decided as to whether or not the abnormality is clinically significant or not clinically significant. A paper copy of each ECG recording should be filed in the patient's medical records. Only overall evaluation (normal/abnormal) will be recorded in the eCRF. If there is a clinically significant abnormal unscheduled ECG finding during the treatment period, this should be recorded on the AE eCRF, according to standard AE collection and reporting processes (see Section 6). If an abnormal ECG finding at screening or baseline is considered to be clinically significant by the Investigator, it should be reported as a concurrent condition. For all ECGs details of rhythm, PR, R-R, QRS and QTc intervals and an overall evaluation will be recorded.

5.2.5 Vital signs

Vital signs to be assessed include: resting heart rate, blood pressure, temperature and weight at the screening visit and at times shown in the study plan. Height will be measured at the screening visit only. Vital signs and weight will be obtained prior to study drug administration according to institutional practice (see Table 1 and Table 2).

5.2.6 Pregnancy test

Pre-menopausal women of childbearing potential must have a negative urine or serum pregnancy test within 3 days prior to starting study treatment. A confirmatory test will be performed before treatment at the start of each cycle, the EOT visit, and the FPV. In the event of suspected pregnancy during the study, the test should be repeated and, if positive, the patient discontinued from study treatment immediately.

5.2.7 Tumour markers

An elevated tumour marker (e.g. CA-125, CEA, PSA) that is used by the investigator to monitor for tumour response will be collected at baseline, Day 1 of each cycle, and at the end of treatment. The results will be recorded in the eCRF. The tumour marker analysis will be performed by a local laboratory.

5.3 Pharmacokinetics

5.3.1 Collection of blood pharmacokinetic samples during safety lead-in (Part A only – closed to enrolment October 2015)

Pharmacokinetic (PK) samples will be collected during the safety lead-in portion of the study during Cycle 1 Day 1 and Cycle 1 Day 3 or Day 10. Steady state PK collections may occur on Day 3 or Day 10 of Cycle 1. The Investigator may select the PK collection day that fits best for the clinic and the patient for the second set of PKs. The date and actual time of the PK sample will be recorded.

Table 4 Cycle 1 Day 1 and Cycle 1 Day 3 or Day 10 safety lead-in PK collections

Time (h) post first AZD1775 dose	0	1	2	4	6	8	12
Swallow AZD1775	X						
PK Sample	X ^a	X ^b	X ^c	X ^c	X ^c	X ^c	X ^c

^a PK sample may be collected the day before dosing.

^b ±5 minutes.

^c ±15 minutes

The timing of the PK samples may be adjusted during the study, dependent on emerging data, in order to ensure appropriate characterisation of the plasma concentration-time profiles.

If a patient misses any doses of AZD1775 a day prior to PK sampling, the Medical Monitor should be contacted regarding the changes required for the timing of the PK assessments. All other assessments, including laboratory safety assessments, vital signs and RECIST should continue to be performed as per study plan, relative to baseline assessments.

Details on sample processing, handling, and shipment are provided in the Laboratory Manual.

5.3.2 Collection of blood pharmacokinetic samples during Part B expansion

PK blood samples will be required from all patients enrolled at approximately 3-5 investigational sites to ensure we have evaluable data from at least 50 patients. These required samples may become optional once there are samples from at least 50 patients. PK blood sampling is highly recommended for all patients at the remaining sites. PK blood sample collections will be taken from consenting patients pre-dose and 2-4 hours post-dose on Day 3 or Day 10 of Cycle 1, Cycle 2, and Cycle 4, and beyond Cycle 4 every 2 cycles. The date and actual time of all PK samples must be recorded.

Table 5 Part B PK collections

Cycle 1, 2, and 4 (and beyond cycle 4 every 2 cycles) Day 3 or Day 10		
Time (h) post first AZD1775 dose	0	2-4 hours
Swallow AZD1775	X	
PK Sample ^a	X	X

^a ±15 minutes

Details on sample processing, handling, and shipment are provided in the Laboratory Manual.

5.3.3 Determination of drug concentration in pharmacokinetic samples

Samples for determination of AZD1775 concentrations in plasma will be analysed by Covance on behalf of Clinical Bioanalysis Alliance, AstraZeneca R&D, using an appropriate bioanalytical method. Full details of the analytical method used will be described in a separate bioanalytical report.

5.3.4 Storage, re-use and destruction of pharmacokinetic samples

Pharmacokinetic (PK) samples will be disposed of after the Bioanalytical Report finalization or six months after issuance of the draft Bioanalytical Report (whichever is earlier), unless requested for future analyses.

Pharmacokinetic samples may be disposed of or destroyed and anonymised by pooling. Additional analyses may be conducted on the anonymised, pooled pharmacokinetic samples to

further evaluate and validate the analytical method. Any results from such analyses may be reported separately from the CSR.

Incurred sample reproducibility analysis, if any, will be performed alongside the bioanalysis of the test samples. The results from the evaluation will not be reported in the Clinical Study Report but separately in a Bioanalytical Report.

Any residual back-up PK samples will be kept in at Covance and will be disposed of after the CSR is finalized.

5.4 Pharmacodynamics

5.4.1 Peripheral blood mononuclear cell (PBMC) samples for pharmacodynamics studies

Peripheral blood mononuclear cell (PBMC) blood samples will be collected in Part B only. A whole blood (8 ml) sample will be drawn for pharmacodynamic analysis at Cycle 1 Day 1 pre-dose, Cycle 1 Day 8 pre-dose, Cycle 2 Day 8 2-4 hours after dosing, and Cycle 4 Day 1 pre-dose.

Details on sample processing, handling, and shipment are provided in the Laboratory Manual.

The results of this PBMC research will be reported separately and will not form part of the CSR.

5.4.2 Repeat biopsies

Part B of the study is designed in part to provide evidence of proof of mechanism (POM). For the Wee1 inhibitor AZD1775, this means to demonstrate that following treatment of patients there is a measurable decrease from baseline in readouts of activity of the Wee1 kinase.

The baseline Wee1 pharmacodynamic (PD) marker pCDK1 (pCDC2) will be retrospectively assessed from the baseline biopsy. A post-treatment biopsy will then be taken after first dose on day 2 or day 3 of the first cycle of treatment.

These paired biopsies will be considered evaluable for POM if assessable by Immunohistochemistry (IHC) for the biomarker above and if the concurrent pharmacokinetic (PK) blood sample is consistent with the patient having had adequate pharmacological exposure to AZD1775.

We estimate that we would need at least 7 patients with evaluable paired biopsies in order to have confidence in an assessment of POM (see statistical calculations below).

A patient showing the target decrease of 50% or more (evaluated as number of cells showing positive staining in post vs pre dose) in pCDK1 will be considered a pharmacodynamic responder. This value is based on preclinical data correlating with anti-tumour efficacy, using the same assay to be used on clinical samples. We have set a POM target value of 50% of

patients having a pharmacodynamic response in their tumour biopsy. With n=7 biopsies, we would accept having established POM if 4 out of the 7 biopsies show the desired biomarker change.

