5.5.5 Archived or recent tumour tissue

A sufficient quantity of archival or fresh tumour tissue must be available to enrol a patient to Part B to identify molecular biomarkers of interest. Molecular biomarker assessments will be performed centrally from archival tumour tissue or from fresh tumour tissue if the latter is being taken for routine clinical purposes and archival tumour tissue is unavailable.

After signing a 'pre-screening' ICF, tumour samples will be submitted for a pathology QC check to ensure that the molecular analysis will be possible with the material provided. If the tumour tissue sample does not pass the QC check, the investigative site will be informed and additional tissue will be requested.

The patients' molecular profiles will be established using a Sponsor-approved method and clinical laboratory (see Laboratory Manual).

All tumour samples will be analysed for a range of cancer-related genes such that clinical response can be correlated to the gene aberrations. TNBC and SCLC biomarker 'positive' cohorts to be analysed include amplifications in CCNE1, MYC, MYCN, or MYCL1.

Biomarker 'negative' is defined as the absence of the qualifying amplification for TNBC or SCLC as specified above. Investigation of biomarker 'negative' results based on emerging signals may be explored through additional expansion cohort(s).

Patients may not have to wait for confirmation of the pathology QC check if genetic profile results are available to confirm the specific biomarker of interest (i.e., *BRCA1* or *BRCA2* genes in ovarian cancer, amplification *CCNE1*, *MYC*, *MYCN*, or *MYCL1* in TNBC or SCLC). The results must be from a certified laboratory and approved by the Sponsor or designee on a case-by-case basis. Submission of archived or fresh tumour tissue to the Central Laboratory will be required. If the tumour sample is considered insufficient by the pathology QC check at the time of analysis the patient will remain on-study.

The preferred tumour tissue samples are block(s) rather than slides, with minimum tumour attributes of $\geq 10\text{mm}^2$ surface area; $\geq 30\%$ tumour cell content, if biopsy, ideally a block contains multiple cores. If a block is unavailable, unstained $5\mu\text{m}$ sections should be provided as follows:

- Large resection >10 slides
- Small biopsy (core needle, bronchial, FNA, effusions) $>15-20$ slides

Please refer to the Laboratory Manual for additional guidance.

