5.5.6 On-treatment tumour biopsy (surface-accessible lesion)

An on-treatment tumour biopsy is required for all patients with surface-accessible lesions, at any time, 12 hours after the third administered dose of AZD1775 on Day 2, or later on Day 3, or during the first 12 hours on Day 4 of Cycle 1 unless medically contraindicated in the opinion of the Investigator.

This biopsy is needed to demonstrate that there is a measurable decrease from baseline in readouts of activity of the Wee1 kinase via analysis of the levels of phosphorylated CDC2 (pCDC2) in tumour samples, following treatment with AZD1775. The collection of baseline and on-treatment biopsies is essential to guarantee the comparison of pCDC2 levels before and during treatment and to provide evidence that patients receive a biologically active dose.

A 'surface accessible lesion' is a lesion that does not require the patient to undergo general anaesthesia for the biopsy procedure, does not require CT-guided interventional radiology involvement and could, for example, be a clearly palpable tumour-involved node or similar.

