5.5.7 Optional biopsies

Optional during this study and will be requested from consenting patients with easily accessible tumours:

- At baseline/screening before dosing
- At the time of disease progression including from consenting patients that continue treatment after the FPV.

Patients will sign a separate informed consent for the tumour tissue biopsies. The tumour biopsy procedure will be performed by core needle, under radiological guidance, or surgically if the site of disease is superficial and palpable or visible. It is mandated that the core biopsy be removed directly from the tumour *in situ* and not cored from a surgically removed tumour. This is to ensure the best possible quality of the biopsy, as the blood/nutrient supply to the tumour is not disrupted prior to biopsy collection.

All tumour biopsies will be collected, stored, and shipped as detailed in the Laboratory Manual.

Any residual samples remaining after analysis will be retained for any potential subsequent retrospective analysis of other response related and/or cancer related biomarkers. It is not intended that data derived from residual sample analysis will be reported in the CSR.

Informed consent must be obtained from any patient who agrees to provide tissue for tumour tissue sample testing.

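### The pharmacodynamic responder rule in Section 5.4.2 counts positive cells with no denominator, so a difference in specimen size alone can create or hide a response

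*Protocol*

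**What the plan says.** Protocol Section 5.4.2 sets the patient-level rule. "A patient showing the target decrease of 50% or more" in pCDK1 counts as a pharmacodynamic responder, and the decrease is "evaluated as number of cells showing positive staining in post vs pre dose". The decision rule across patients follows: "With n=7 biopsies, we would accept having established POM if 4 out of the 7 biopsies show the desired biomarker change".

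Evaluability is defined in the same section: "These paired biopsies will be considered evaluable for POM if assessable by Immunohistochemistry (IHC) for the biomarker above", provided the accompanying PK sample shows sufficient exposure. It sets no minimum number of tumour cells, scored area or size match. On the 50% cut the section says: "This value is based on preclinical data correlating with anti-tumour efficacy, using the same assay to be used on clinical samples". It does not say whether the assay result is expressed per cell scored.

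The other relevant sections add no denominator:

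- Section 5.5.6 requires the on-treatment biopsy in patients with surface-accessible lesions and says: "The collection of baseline and on-treatment biopsies is essential to guarantee the comparison of pCDC2 levels before and during treatment". It fixes neither the sampling method nor the specimen size.
- Section 5.5.7, on the optional biopsies that include the baseline sample, says: "The tumour biopsy procedure will be performed by core needle, under radiological guidance, or surgically if the site of disease is superficial".
- Section 8.9 gives the statistics for 7 pairs: a target response rate of 50%, an uninteresting rate of 25%, and error probabilities of 20% (false positive) and 10% (false negative). It does not redefine response.

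**The concern.** Wee1 inhibition should lower the fraction of tumour cells that stain for pCDK1. The number of positive cells on a slide also depends on how much tumour was sampled, and nothing in the protocol holds that constant between the two biopsies. A pair of unequal size is not excluded, because it can still be assessed by IHC.

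With only seven pairs and a cut at four, one or two size artefacts in either direction can change the conclusion. Proof of mechanism could be accepted partly on tissue quantity, or missed although the drug was working.

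**Working it through.** **1. The plan's own figures (Section 8.9).** Exact binomial calculations reproduce them.

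- 4/7, lower one-sided 80% bound: 35.0% (stated 35%).
- 1/7, upper one-sided 90% bound: 45.3% (stated 45%).
- 4/7, two-sided 80% interval: 27.9% to 83.0% (stated 27% to 83%; the lower limit looks truncated).
- P(at least 4 of 7 | 25%) = (945 + 189 + 21 + 1)/16384 = 7.1%, within the 20%.
- P(at most 1 of 7 | 50%) = 8/128 = 6.3%, within the 10%.

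The binomial arithmetic is sound. The question is what is being counted.

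**2. What the count measures.** Let N be the tumour cells on the section and f the fraction positive. Then

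count ratio = (N_post × f_post) / (N_pre × f_pre).

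If f is unchanged, this is N_post/N_pre, the specimen-size ratio. Two illustrative cases:

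| | Pre | Post | Change in count | Change in fraction | Result under 5.4.2 |
|---|---|---|---|---|---|
| No inhibition, less tissue | 2000 × 40% = 800 | 1000 × 40% = 400 | −50% | 0 | Responder |
| Inhibition, more tissue | 1000 × 40% = 400 | 2000 × 15% = 300 | −25% | −62.5% | Non-responder |

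This step needs no distributional assumption.

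**3. How often it could matter.** The protocol gives no figure for specimen-size variation, so the following is assumed: no drug effect, tumour-cell numbers lognormal with the same CV in each specimen, pre and post independent, and median post/pre size ratio m. Then

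- s² = ln(1 + CV²)
- q = P(chance responder) = Φ[(ln 0.5 − ln m) / (s√2)]
- P(rule fires) = P(Bin(7, q) ≥ 4)

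Example: CV 100%, m = 1. s = √(ln 2) = 0.833, s√2 = 1.177, q = Φ(−0.693/1.177) = Φ(−0.589) = 0.278, and P(rule fires) = 0.099.

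| Median size ratio m | CV | q per patient | P(at least 4 of 7) |
|---|---|---|---|
| 1.0 | 25% | 2% | <0.1% |
| 1.0 | 50% | 15% | 1.2% |
| 1.0 | 75% | 23% | 5.5% |
| 1.0 | 100% | 28% | 9.9% |
| 0.75 | 25% | 12% | 0.6% |
| 0.75 | 50% | 27% | 9.3% |
| 0.75 | 75% | 33% | 17% |
| 0.75 | 100% | 37% | 23% |
| 0.5 | any | 50% | 50% |

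**4. The same situation scored as a percentage.** A simulation used a median of 1000 tumour cells at baseline and 1000 or 500 on treatment, f of 0.1, 0.2 or 0.4, and CV 50% or 100%. With no drug effect, the chance of a 50% fall in the percentage positive was at most about 0.5%. The raw count gave about 15% to 50% in the same scenarios. Only counting error was simulated; staining and reader variation were not.

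**The case against.** The strongest reply is that a short parenthesis is being read as a full scoring specification. Section 5.5.6 speaks of levels of pCDC2, the sponsor already has an assay, and scoring detail usually sits in a laboratory manual that is not shown. That manual may fix the number of cells or fields scored, or the authors may have meant a percentage. This is possible, and it limits what can be said about what the laboratory does. It does not repair the text: 5.4.2 is the only operational definition of response in the protocol, and it names a count.

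A reader might also infer that the 4-of-7 rule is badly inflated. Section 5.5.5 admits tissue as different as a large resection and "Small biopsy (core needle, bronchial, FNA, effusions". If on-treatment specimens held a half, a third or a quarter as many tumour cells, the rule would fire with no drug effect in 50%, 78-91% and 90-99% of cases (the ranges are for CV 50-100%). The document does not support that reading. The list in 5.5.5 concerns archival or routine tissue for molecular profiling, not the paired biopsies. Section 5.5.7 further requires cores to be taken from the tumour in place, not from a resected specimen. Core against surgical sampling leaves room for some mismatch, but nothing establishes a systematic shortfall.

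Two further points stand. With no systematic difference, the rule's false-positive probability stays within the stated 20%, and positive correlation between the two specimen sizes in a patient would lower it. The consequence is also limited: proof of mechanism is not among the objectives in Section 2, Section 8.3 plans no formal testing, the Part B dose came from Part A (Section 7.2.2), and no dose, cohort or stopping decision is tied to the 4-of-7 result.

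**Conclusion.** The concern holds as a defect in the stated responder rule. Followed as written, the rule can label a patient a responder with an unchanged positive fraction, and a non-responder after a 62.5% fall in that fraction.

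The likely size is moderate. With no systematic size difference and CV 50-100%, chance response is about 15-28% per patient, around the 25% that Section 8.9 regards as uninteresting, and the 4-of-7 rule fires falsely about 1-10% of the time. Among the scenarios examined, the 20% limit is passed only with systematically smaller on-treatment specimens: 23% at a median of 25% fewer cells with CV 100%, and 50% at half as many. All these rates rest on assumed, independent, lognormal specimen sizes; the worked example does not. ORR, DCR, DoR and PFS are not affected.

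**What to change.** In Section 5.4.2:

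1. Replace the count in the parenthesis with the percentage of tumour cells that stain positive, and define response as a relative decrease of at least 50% in that percentage from baseline.
2. Confirm that the preclinical 50% threshold was set on that same scale. H-score should not be offered as an interchangeable alternative: it also weights intensity, so a 50% fall in H-score is not the same as a 50% fall in percentage positive.
3. Add to the evaluability condition a minimum number of scorable tumour cells in both specimens, set by the assay laboratory. The protocol gives no basis for a particular number.

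The slides and the IHC assay stay the same. The cost is a small text change, the check on the preclinical scale, and possibly a few sparse pairs becoming non-evaluable, which matters somewhat when at least seven evaluable pairs are needed. If the laboratory already scores a percentage, the change only brings the protocol into line with practice.
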